6.6 Infant Monthly Visits and Study Exit Visit

Infants will be followed monthly for the first 24 weeks of life. Infants will be assessed at each visit for TB exposure and signs and symptoms suggestive of TB disease. The mother's visits and the infant's visits will ideally be scheduled to occur on the same day.

There is no required sequencing of procedures at these visits.

The final study visit for infants will occur at 24 weeks of life.

Infant Monthly Visit and Study Exit Visit Procedures (± 2 weeks)	
Administrative and Regulatory	
 • None
Clinical	
 • Limited physical exam • Record medical and medications history • Record/update AEs • Provide available test results to mother • Assess TB symptoms, risk and exposure
Laboratory	Collect blood for (no blood is collected at the Study Exit Visit): 
 • Complete blood count (if clinically indicated) • Liver Function Test (if clinically indicated) • Coagulation profile (if clinically indicated)

6.7 Clinical Evaluations and Procedures

Additional clinical assessments may be performed at the discretion of the examining clinician in response to symptoms or illnesses present at the time of the exam.

6.7.1 Clinical assessment for development of TB disease

TB symptoms, risk, and exposure will be assessed for each participant (i.e., women and infants) at each study visit. A pulmonary and lymph node exam will be conducted for participants with suspected TB disease.

For women, the WHO TB symptom screen will be used. In addition, failure to have adequate weight gain in pregnancy will be recorded.

For infants, TB will be assessed by known exposure or with the following symptoms: cough, respiratory distress, failure to gain weight, weight loss, or fever.

See Section 8.1 for details regarding participant management of suspected and confirmed TB disease. The IoR/designee may conduct additional testing and confirmatory procedures per local standard of care for infants suspected of developing TB disease. Participants will remain on-study for follow-up visits.

All participants (i.e., women and infants) confirmed with active TB disease will be referred to local standard of care for treatment. Infants of mothers who develop active TB will also be referred for evaluation and initiation of TB preventive therapy as per local pediatric TB guidelines.

6.7.2 Physical Examination

Maternal complete physical examination:

For women, a complete physical exam will include the following: vital signs (temperature, pulse, blood pressure, and respiration), assessment of general appearance, cardiac exam, pulmonary exam, lymph node exam, and liver and spleen size per abdominal exam. Weight (so BMI and change in weight can be calculated) and mid-upper arm circumference (MUAC) will also be measured. Height will be assessed at the Entry Visit only.

Maternal targeted physical examination:

For women, a targeted physical exam during study follow-up will include vital signs (temperature, pulse, blood pressure, and respiration) and weight. Additional assessments should be driven by any previously identified or new signs or symptoms including diagnoses that the woman has experienced since the last visit.

Infant complete physical examination:

For infants, at the Newborn Visit, a complete physical exam will include the following: APGAR scores, birth weight and length, head circumference, gestational age, congenital abnormalities, demographics.

Infant limited physical examination:

For infants, at the monthly study visits, a limited physical exam will include the following: Weight (documented on a growth chart), length, head circumference, and vital signs (temperature, heart rate, and respirations). Additional assessments should be driven by any previously identified or new signs or symptoms including diagnoses that the infant has experienced since the last visit.

6.7.3 Obstetrical Exam to Assess Fetal Health: Mothers

At the Screening Visit, an obstetrical exam will be conducted to assess the following:

- Gestational age, presence of severe fetal abnormalities, and presence of multiple births, by ultrasound
- Fetal heart sounds confirmed on Doppler or fetal movements felt by mother

The Entry Visit and follow-up visits will include the following assessments until the mother delivers:

- Fetal heart sounds confirmed on Doppler or fetal movements reported by mother

6.8 Laboratory Evaluations and Procedures

Test results obtained from standard of care visits within 14 days of the participant's monthly study visit will be used. Lab evaluations must be performed in DAIDS-approved laboratories that are participating in an external quality assurance (EQA) program.

Note: NIH recommendations for maximum pediatric and adult blood draw volumes will be followed in this study. For women, the volume of blood drawn shall not exceed 10.5 mL/kg or 550 mL, whichever is smaller, over any eight week period. For infants, the volume of blood drawn at any study visit should not exceed 5 mL/kg in a single day and 9.5 mL/kg over any eight-week period. The priority order of sample collections will be as follows: samples needed for clinical safety assessments/AEs will be collected first (specific tests as determined by investigator), followed by samples needed for PK analysis.

6.8.1 Laboratory Evaluations

Normal laboratory ranges will be the institutional values at the clinical research site. If a site does not have normal laboratory ranges, per an IMPAACT memorandum dated 11 December 2009, the site laboratory may adopt established ranges from another study or laboratory without verification. The medical director of the laboratory is responsible for the adoption of external unverified ranges, and s/he must provide reasonable evidence that the ranges are appropriate. Documentation of "reasonable evidence" may include the opinions of one or two local pediatricians, pathologists, or other knowledgeable laboratory personnel.

For the maternal laboratory evaluations, the following will be recorded on the case report forms (CRFs):

- Complete blood count will include white blood count, hemoglobin and platelets.
- Liver function tests will include albumin, AST, ALT, and total bilirubin.
- Coagulation profile will assess Prothrombin Time (PT) only.

For women, blood will be collected at the Entry Visit for later testing of HBs AG, HBs Ab, HCV Ab, as determined by the Core Team.

For the infant laboratory evaluations, the following will be recorded on the case report forms (CRFs):

- A coagulation profile to assess PT will be collected at the Newborn Visit only if the mother is still on the study drug regimen.
- Complete blood count will include white blood count, hemoglobin and platelets, if indicated based on symptoms.
- Liver function tests will include albumin, AST, ALT, and total bilirubin, if indicated based on symptoms.

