- One quantitative HIV RNA PCR (above the limit of detection for evidence of infection)
- One qualitative HIV RNA PCR
- One HIV total nucleic acid test

If Sample #1 is negative, the participant should be enrolled as HIV-1-uninfected with testing repeated as clinically indicated. If Sample #1 is positive, then collect and test Sample #2.

- Sample #2 must be tested in a CAP/CLIA-approved laboratory (for US sites) or in a laboratory that operates according to GCLP guidelines and participates in appropriate external quality assurance program (for international sites).
 - Sample #2 may be tested using any of the following:
 - Rapid antibody test. If this option is used in combination with two rapid tests for Sample #1, at least one of the three rapid tests must be FDA-approved, and the third rapid test must be from a third manufacturer or based on a third principle or epitope.
 - One EIA OR Western Blot OR immunofluorescence OR chemiluminescence
 - One HIV DNA PCR
 - One quantitative HIV RNA PCR (above the limit of detection for evidence of infection)
 - One qualitative HIV RNA PCR
 - One HIV total nucleic acid test
- 4.1.5 If HIV-1-infected, documented current prescription of EFV + 2 NRTI regimen and reports taking regimen for at least two weeks prior to enrollment (regimens containing protease, integrase, or entry inhibitors are not permitted)
- 4.1.6 Documented laboratory values obtained within 30 days prior to enrollment:
- Hemoglobin ≥ 7.5 g/dL
 - ALT ≤ 3 times the upper limit of normal (ULN)
 - Total bilirubin ≤ 2.5 times the ULN
 - Absolute neutrophil count (ANC) ≥ 750 cells/mm³
 - Platelet count $\geq 100,000$ /mm³
- 4.1.7 Per participant report at screening, intent to remain in the current geographical area of residence for the duration of the study
- 4.1.8 Per participant report at screening, able to swallow whole tablets
- 4.1.9 Per participant report, intention to keep the pregnancy
- 4.1.10 Per participant report, willingness to permit infant to participate in the study

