Laboratory	Blood	Collect blood for: 
 • Sparse PK sample collection (during the visit of the last dose and 48 hours following) • Plasma sample collection (breast milk PK participants only, conducted first and second week postpartum) • Complete blood count (every four weeks) • Liver Function Test (every four weeks) • Coagulation profiles (at one visit at ≥34 weeks gestational age only)
	Breast milk	Collect breast milk for: 
 • Breast milk PK sample collection (if eligible, conducted first and second week postpartum and on the visit of the last dose)
Study Product		
 • Prescribe (according to local guidelines) and administer RPT, INH, and pyridoxine under DOT

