8.1.2 Rifamycin hypersensitivity syndrome (RHS)

For women who develop signs or symptoms suggestive of RHS (e.g., fever, myalgia, rash, hypotension, clinical hepatitis):

- Hold study drug regimen
- Assess the women for RHS (see note below for definition) through clinical evaluation and laboratory testing, including comprehensive metabolic panel, CBC with manual differential, and other tests that, at the discretion of the site IoR/designee, are necessary to exclude likely alternative diagnoses (e.g., should symptoms suggest influenza, a nasopharyngeal aspirate for viral testing could be sent).
- If \geq Grade 2 AE or toxicity meets the case definition for RHS, permanently discontinue the study drug regimen and notify the Core Team.

In the event of treatment discontinuation, participants will remain on-study and continue to be followed through 24 weeks postpartum.

Note: RHS is defined as follows:

- Hypotension, urticaria, angioedema, acute bronchospasm, conjunctivitis, thrombocytopenia, or neutropenia that occurred in relation to study drug regimen; *or*
- More than four of the following that occurred in relation to study drug (one of which must be assessed as having been > Grade 2): weakness, fatigue, muscle pain, nausea, vomiting, headache, fever, aches, sweats, dizziness, shortness of breath, flushing, rash, itching, syncope, cough, palpitations, chills, or eosinophilia.
- A complete listing of RHS symptoms reported by the woman should be recorded on the appropriate CRFs.

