9.2.1.2 Safety (maternal)

- Incidence of related serious adverse events (SAEs) in pregnant and postpartum women taking once-weekly RPT + INH
- Grade 2 adverse events (AEs) judged to be related to study drug regimen
- All Grade 3 and 4 AEs
- All serious AEs
- All AEs leading to permanent discontinuation of study drug regimen (i.e., RPT, INH, and pyridoxine)

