13.5 Potential Risks

The potential risks of this study are those associated with having blood drawn, treatment failure, resistance to TB medications, suboptimal dosing for latent TB, possible reactions to the RPT + INH investigational product and breach of confidentiality.

Drawing blood may cause transient discomfort and fainting. Fainting is typically transient and managed by having the participant lie down. Bruising at the blood draw site may occur, but can be prevented or lessened by applying pressure to the draw site for several minutes. There is a slight risk of infection associated with drawing blood.

A chest x-ray may be indicated to confirm active TB disease. The radiographic exposure required is minimal and is far below the maximum allowed, even for pregnant women. Therefore, this procedure is associated with minimal risk.

The following side effects have been associated with the use of RPT:

- Rash
- Reddish coloring of urine, sweat, sputum, saliva, tears, and breast milk. Contact lenses and dentures may be permanently stained.
- Liver damage that may include abnormal liver function tests. If you develop any of the following symptoms of liver damage, you should call your doctor right away:
 - Unexplained loss of appetite
 - Pale-colored stools
 - Yellowing of the eyes or skin
 - Pain in the upper abdomen
 - Dark urine
 - Loss of appetite
 - Low blood counts (for example, for the blood cells that help your body fight infection)
 - Dizziness
 - Hypertension
 - Headache
 - Low blood sugar
 - Upset stomach or vomiting

- Decreased effectiveness of hormonal contraceptives and other medications. Tell your doctor about all medications that you are taking.

Women taking rifapentine may have a serious allergic reaction called Rifamycin Hypersensitivity Syndrome (RHS) that can be dangerous if not caught right away. Women will be told to report to the study clinic as soon as possible for an evaluation if they report any of the symptoms (defined in Section 8).

When administered during the last few weeks of pregnancy, rifampin, another rifamycin product, has been shown (in rare cases) to increase the risk of maternal postpartum hemorrhage and bleeding in the exposed neonate (see Section 8.1.10).

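### After enrollment, no scheduled maternal blood count specifies a neutrophil count, although neutropenia alone can meet the trial's definition of rifamycin hypersensitivity

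*Protocol*

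**What the plan says.** Protocol 6.8.1 sets out which maternal laboratory results go on the case report form (CRF). For the blood count it says: "Complete blood count will include white blood count, hemoglobin and platelets". No differential or absolute neutrophil count (ANC) is listed.

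Blood counts are scheduled at screening (6.1), every four weeks while on study drug (6.3) and at the monthly visits after the regimen, apart from the exit visit, when no blood is taken (6.4). Appendix I-A repeats this schedule with a 3 mL sample each time. None of these places adds a differential.

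Neutrophils do appear elsewhere in the protocol:

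- Inclusion criterion 4.1.6 requires a documented ANC of at least 750 cells/mm³ within 30 days before enrollment.
- Section 8.1.2 gives, as the first limb of the RHS definition: "Hypotension, urticaria, angioedema, acute bronchospasm, conjunctivitis, thrombocytopenia, or neutropenia that occurred in relation to study drug regimen". Any one of these is enough. An event of Grade 2 or higher that meets the definition leads to permanent discontinuation. Eosinophilia is one of the items in the second limb.
- Section 8.1.2 also asks for a blood count with manual differential as part of the RHS work-up, for women who already have suggestive signs or symptoms.

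The primary maternal safety outcomes in 9.2.1.2 include "All Grade 3 and 4 AEs".

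**The concern.** The protocol treats neutrophils as important enough to restrict entry and to define a stopping event, but names no neutrophil measurement at any scheduled visit between those two points. Thrombocytopenia stands in the same RHS limb, and platelets are recorded at every scheduled blood count. The protocol gives no reason for treating neutrophils differently.

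What is at stake is how completely a primary outcome is ascertained. A laboratory-only event reaches the Grade 3 and 4 tally only if somebody measures it. If a differential is reported where the local laboratory happens to supply one and not elsewhere, ascertainment will depend on the site. The sites are spread over seven countries (section 4), so uniform laboratory practice cannot be presumed. Under 9.7.2 the proportion of women with Grade 3 or higher or serious events is reported overall and by cohort, with exact 95% confidence intervals, and those intervals do not reflect events that were never measured.

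**Working it through.** The main check is a comparison of sections; the documents contain no figure for neutropenia to recompute.

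**Step 1. Where a neutrophil count is specified**

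| Time point | Blood count scheduled | Neutrophils specified |
|---|---|---|
| Eligibility, up to 30 days before enrollment (4.1.6; screening count in 6.1) | Yes | Yes, by 4.1.6; not in the 6.8.1 list |
| On drug, every four weeks (6.3) | Yes | No |
| Monthly visits after the regimen (6.4) | Yes | No |
| Suspected RHS (8.1.2) | For cause | Yes, manual differential |

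The two specified measurements are a pre-enrollment value and a symptom-triggered one. Neither is scheduled monitoring after enrollment.

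**Step 2. Whether the RHS work-up covers asymptomatic cases**

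Its entry condition is signs or symptoms suggestive of RHS; the examples given are fever, myalgia, rash, hypotension and clinical hepatitis. A woman whose only abnormality is a low neutrophil count has none of these examples.

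**Step 3. Whether the recorded white count can stand in for the ANC**

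ANC = total white count × neutrophil fraction. As an illustration with assumed values, 4,000/mm³ × 0.15 = 600/mm³, which is below the entry limit of 750. At the same total count, the limit corresponds to a neutrophil fraction of 750 / 4,000 = 18.75%. The white count carries some information, but the ANC cannot be recovered from it.

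**Step 4. Whether the general recording rule closes the gap**

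Section 7.2 records all protocol-specified laboratory results and sends every Grade 3 or higher result for further evaluation. It acts on results that exist. After enrollment no scheduled ANC is specified, so the rule has nothing scheduled to act on for this event.

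**Step 5. How much a single missed event would matter**

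Section 9.5.2 says that with 25 women, zero events gives a 95% upper bound of approximately 15%, and two events a bound in the vicinity of 30%. The exact two-sided bound for zero events is 1 − 0.025^(1/25) = 13.7%, close to the stated figure. The exact (Clopper-Pearson) upper bounds are the 97.5th percentiles of Beta(x + 1, 25 − x):

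| Events among 25 | Point estimate | Exact 95% upper bound |
|---|---|---|
| 0 | 0% | 13.7% |
| 1 | 4% | 20.4% |
| 2 | 8% | 26.0% |

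These figures show how sensitive the reported result is to one or two events. They do not predict how many would be missed.

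**The case against.** Several stronger readings are tempting, and the documents do not support them.

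- **Neutropenia is not monitored at all.** The list in 6.8.1 governs CRF recording, not what a laboratory measures or a clinician sees. A site may receive a differential, and 7.2 would then give a Grade 3 or higher result a route onto an event form. The Laboratory Processing Chart and the Manual of Procedures, which are not among the documents, may add detail.
- **There is no recorded baseline.** Criterion 4.1.6 requires an ANC, and 7.2 calls for all protocol-specified screening results to be recorded. The supportable statement is that 6.8.1 does not list it, so the two sections need reconciling.
- **The RHS rule cannot be triggered by neutropenia.** A differential is required once RHS is suspected, and section 7 counts an abnormal laboratory finding as a possible sign, so a low total white count could arguably prompt the work-up. The rule also depends on Grade 2 or higher and on relation to study drug.
- **A named drug risk goes unmonitored.** Section 13.5 speaks of low blood counts, with infection-fighting cells as the example. The white count is scheduled and recorded, and it monitors that risk in part.
- **The hypersensitivity rate gives the scale.** Protocol Table 1 reports possible hypersensitivity in 85/1861 = 4.6% of HIV-negative participants, but 1% and 0% in the two HIV-positive groups. None of these is a neutropenia rate.
- **Reported safety will look better than it is.** With no neutropenia rate in the documents, the effect could be zero.

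All of these objections stand against the stronger readings. None supplies a scheduled post-enrollment neutrophil count.

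**Conclusion.** The point holds as a gap in specification that bears on a primary safety outcome. As written, the plan names no neutrophil count at any scheduled maternal visit after enrollment, although it uses neutrophils to decide entry and to define RHS. Asymptomatic Grade 3 or 4 neutropenia may be missed or unevenly captured.

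The size is unknown. The direction, if there is an effect, is towards under-reporting. The conclusion assumes that sites follow the protocol's lists literally and that no unseen laboratory document already requires a differential; if one does, the remaining defect is that the CRF list omits it. The change is worth making because it costs little and the cohorts are small enough for single events to matter. Nothing here shows that the regimen's safety is misjudged.

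**What to change.** 1. In 6.8.1 and Appendix I-A, specify the scheduled maternal blood count as one with differential, run on the 3 mL sample already planned.
2. Record ANC and eosinophils on the CRF at screening, every four weeks on drug, and at the monthly visits where a blood count is drawn. Eosinophils are included because eosinophilia is a second-limb RHS item.
3. Reconcile 4.1.6, 6.8.1, 7.2 and 8.1.2 so that the eligibility ANC, the recorded results and the RHS definition refer to the same measurement.
4. Leave every hold and discontinuation rule as it stands. This is a change to measurement and recording only.

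The cost is a short text change and two CRF fields, with no added visit or blood volume. The real downside is more laboratory events to grade and attribute: entry is allowed down to 750 cells/mm³, so some low values will need a judgment on relatedness that feeds the existing rules in 8.1.2 and 8.1.12. Infant blood counts need no change on this ground, because the RHS section applies to women and the protocol sets no infant neutrophil criterion.

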6.8.2 PK Specimen Collection

Details regarding the Intensive, Sparse, and breast milk PK specimen collections (and the optional cord blood collection) for women, as well as the single PK specimen collection for infants are included in Section 10.

6.8.3 Specimen Preparation, Testing, Storage, and Shipping

The IMPAACT 2001 Laboratory Processing Chart (LPC) provides instructions regarding the collection, processing, and shipping of specimens for this study and is available on the IMPAACT website.

6.8.4 Biohazard Containment

As the transmission of HIV and other blood-borne pathogens can occur through contact with contaminated needles, blood, and blood products, appropriate blood and secretion precautions will be employed by all personnel in the drawing of blood and shipping and handling of all specimens for this study, as currently recommended by the CDC and the National Institutes of Health. All dangerous goods materials, including diagnostic specimens and infectious substances, must be transported using packaging mandated by CFR 42 Part 72.

All infectious specimens will be sent using packaging that meets requirements specified by the International Air Transport Association Dangerous Goods Regulations for UN 3373, Biological Substance, Category B, and Packing Instruction 650. Refer to individual carrier guidelines (e.g., Federal Express or Airborne) as well as specific requirements of the host country for specific instructions required for ground transportation within that country.

Infection control for active TB cases and good laboratory practices for TB isolation will be according to WHO guidance and best practices locally to minimize TB transmission. Please refer to instructions detailed in the International Air Transport Association (IATA) Dangerous Goods Regulations.

